#### ***11.4 Consent Processes and Documents***

All patients will be thoroughly screened prior to admission onto this study. During this time, the patient, along with family members, will be presented with a detailed description of the protocol treatment. The specific requirements, objectives, risks and benefits will be reviewed with the patient. The Informed Consent document will be given to the patient and they are asked to review it and ask questions prior to agreeing to participate in this protocol. The patient will be reassured that participation on this trial is entirely voluntary and that they can withdraw or decide against treatment at any time without adverse consequences. The Principal Investigator or their designee is responsible for completing the consent process and a copy of the completed Consent Document is offered to the patient.

#### ***11.5 Recruitment Strategy***

Patients, their physicians or family members may contact the Principal Investigator or a designated associate investigator responsible for this protocol. Given the large number of patients with melanoma and the limited therapy available for advanced disease, we believe recruitment for this trial will be rapid. An IRB approved informational mailing announcing the availability of this study will be sent to the clinical oncology community. The study will be registered with the clinicaltrials.gov website database.

#### ***11.6 Patient Confidentiality***

Strict patient confidentiality is standard policy at the participating clinical sites. Standard practices will be strictly followed and adhered to.

## **12 STATISTICAL CONSIDERATIONS**

### ***12.1 Sample Size***

This study was originally designed to compare the response rates between the combined dorgenmeltucel-L plus immune checkpoint therapy arm to the immune checkpoint therapy arm alone. During this study, enrollment will include a total of 100 evaluable patients across 2 treatment arms (50:50).

Assuming a disease control rate of 22% (Wolchok *et al.*) in the immune checkpoint monotherapy arm and a combined arm response rate of 42%, a total of 100 patients (1:1 ratio) will be required to assess superiority of response rate with 80% power and two-sided alpha of 0.20.

As the primary endpoint has been changed from overall response rate to PFS, 50 patients per treatment arm (100 patients total) will provide 70% power to detect a hazard ratio of 0.6895 and 80% power to detect a hazard ratio of 0.6435, assuming the immune checkpoint monotherapy control arm has a median time to disease progression of 3 months and a two-sided type I error rate of 0.20. A total of 96 events are required for analysis.

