***PROTOCOL SYNOPSIS:***

Title: A Phase 2b Study of Immune Checkpoint Inhibition With or Without Dorgenmeltucel-L (HyperAcute Melanoma) Immunotherapy for Patients with Stage IV Melanoma

Primary Objectives: *Safety:* To determine the safety of administration of immune checkpoint inhibition with or without dorgenmeltucel-L (HyperAcute Melanoma (HAM)) immunotherapy for patients with Stage IV melanoma.

*Efficacy:* To assess the progression-free survival (PFS) of metastatic melanoma patients treated with immune checkpoint inhibition with or without dorgenmeltucel-L immunotherapy.

Secondary Objective: *Efficacy:* To assess the overall response rate, duration of response, duration of stable disease, and overall survival (OS) of patients with Stage IV melanoma treated with immune checkpoint inhibition with or without dorgenmeltucel-L immunotherapy.

*Biologic activity:* To measure possible anti-tumor immune responses in melanoma metastases in patients. To further determine whether the humoral and cellular mediated arms of the host immune system are activated secondary to dorgenmeltucel-L combined with immune checkpoint inhibition. Lastly, to perform correlative studies of patient blood samples (and tumor when available) to determine the mechanism of any observed anti-tumor effect.

Population: Patients with Stage IV metastatic melanoma  
**Arm 1:** Patients will receive immune checkpoint inhibition plus dorgenmeltucel-L  
Immune checkpoint inhibition consists of the treating physician's standard of care choice of ipilimumab, nivolumab, or pembrolizumab.  
**Arm 2:** Patients will receive immune checkpoint inhibition alone  
Immune checkpoint inhibition consists of treating physician's standard of care choice of ipilimumab, nivolumab, or pembrolizumab.

Sample Size: One hundred total patients will be randomized with equal allocation to Arm 1 (50 patients) and Arm 2 (50 patients). Patients will be stratified by immune checkpoint therapy and disease status and categorized as follows:

- 1) Immune checkpoint inhibition
- 2) Patients with unresectable advanced disease
- 3) Patients with resectable advanced disease who receive the immunotherapy in advance of resection

- 4) Patients with resected isolated advanced disease who are treated in a no apparent disease (NAD) state

Investigational Drugs:

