#### 4.4 *Duration of Therapy*

Patients whose tumor progresses on therapy will be off-study. However, mild progression ( $\leq 25\%$  increase in tumor size) at the beginning of the treatment is allowed, given the usual delayed response / pseudoproggression seen with immunotherapy (Wolchok et al., 2009).

Patients who experience a SAE which triggers stopping rules for immune checkpoint inhibitors ipilimumab, nivolumab, or pembrolizumab as described in their respective package inserts will be permanently discontinued from the immune checkpoint inhibitor. They can be continued on dorgenmeltucel-L (if in Arm 1) once recovered from immune checkpoint inhibitor toxicity.

Patients are also off study who:

- experience intercurrent illness that prevents further administration of treatment;
- decide to withdraw from the study;
- experience general or specific changes in the patient's condition that render them unacceptable for further treatment in the judgment of the investigator.

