**Follow Up Visits for ALL Subjects (after 1st FUV):**

- Imaging to be completed every 3 months until disease progression, after disease progression imaging is completed per standard of care
- Survival status checks to be completed at least every 3 months until death or lost to follow up
- All other assessments should be completed per standard of care practices.

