### **Populations to be Analyzed**

The primary population for efficacy will be the full analysis set (FAS), defined as all randomized subjects. In the FAS patients will be analyzed in the treatment group to which they were assigned.

The primary population for safety analyses will be the safety analysis set, defined as all randomized subjects who receive at least one administration of study treatment (dorgenmeltucel-L or immune checkpoint therapy).

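### Section 12.1 requires 96 PFS events from 100 randomised patients, leaving room for only four without an event, with no loss allowance and no fallback cut-off

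*Combined protocol and SAP*

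**What the plan says.** The synopsis fixes the sample size: "One hundred total patients will be randomized with equal allocation to Arm 1 (50 patients) and Arm 2 (50 patients". Section 12.1 words it differently: "enrollment will include a total of 100 evaluable patients across 2 treatment arms (50:50". For PFS, Section 12.1 claims 70% power at a hazard ratio of 0.6895 and 80% at 0.6435, with a two-sided type I error of 0.20, "assuming the immune checkpoint monotherapy control arm has a median time to disease progression of 3 months". It then states: "A total of 96 events are required for analysis".

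On who is analysed, Section 12.3 (Populations to be Analyzed) says: "The primary population for efficacy will be the full analysis set (FAS), defined as all randomized subjects". On observation, Section 8 (Follow Up Visits for ALL Subjects) says: "Imaging to be completed every 3 months until disease progression", and "Survival status checks to be completed at least every 3 months until death or lost to follow up". Section 4.4 lists patients who "decide to withdraw from the study" among those who go off study. Section 12.3 (Missing Data) censors subjects without efficacy evaluations at time 0, and leaves imputation rules for specific efficacy endpoints to the statistical analysis plan. Section 12.2 puts no cap on any disease-status stratum, including patients treated with no apparent disease.

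**The concern.** An event-driven analysis needs either spare patients or a second route to the cut-off. Here 96% of randomised patients must have an observed event and there is no second route. The plan itself names ways in which a patient can end without one: full withdrawal, loss to follow-up, and censoring at time 0. Patients treated with no apparent disease, and durable responders, would have events late.

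If the count stalls below 96, the condition for the primary analysis is never met. The sponsor would then have to pick a data cut-off with no prespecified rule. The trial is open-label (Section 12.2), so that choice could be made with knowledge of outcomes by arm.

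**Working it through.** **Inputs from the protocol.** 100 patients, 1:1 (Synopsis); hazard ratios (HR) 0.6435 and 0.6895, power 80% and 70%, two-sided alpha 0.20, control median 3 months, 96 events (Section 12.1); analysis of all randomised subjects (Section 12.3). **Assumed, because the documents give no figure:** loss rates, accrual period, and the share and median of no-apparent-disease patients.

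**1. Reproduce the 96.** Freedman's formula for 1:1 allocation: events = (z₀.₉₀ + z_power)² × ((1 + HR)/(1 − HR))².
- HR 0.6435, 80% power: (1.2816 + 0.8416)² × (1.6435/0.3565)² = 95.8.
- HR 0.6895, 70% power: (1.2816 + 0.5244)² × (1.6895/0.3105)² = 96.6.

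The figure of 96 is reproduced.

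**2. Room for patients without an event.** 100 − 96 = 4.

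**3. The plan's own assumptions, no loss.** With exponential PFS, the monthly hazard is ln 2/3 = 0.2310 in control and 0.2310 × 0.6435 = 0.1487 in the combination arm. Expected events when every patient has t months of follow-up are 50(1 − e^(−0.2310t)) + 50(1 − e^(−0.1487t)). This gives 88.5 at 12 months, 95.8 at 18 and 98.4 at 24, and reaches 96 at 18.3 months. The chance of at least 96 by 24 months, from the sum of the two binomial counts, is 97.8%.

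**4. A few patients never observed to have an event.** Let each patient independently have an assumed chance q of this. The chance of missing 96 is P(Bin(100, q) ≥ 5):

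| q | 2% | 3% | 5% | 10% |
|---|---|---|---|---|
| Chance of missing 96 | 5% | 18% | 56% | 98% |

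**5. The same risk as a yearly loss rate.** With event hazard l and loss hazard g = −ln(1 − yearly loss)/12, the chance that a patient ever has an observed event is l/(l + g). Chance of ever reaching 96 at HR 0.6435:

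| Control median | 5% yearly loss | 10% yearly loss |
|---|---|---|
| 2.8 months | 93% | 56% |
| 3 months | 92% | 51% |
| 4.1 months | 80% | 25% |

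The 2.8- and 4.1-month medians are those quoted in Section 2.5 for ipilimumab and 3-weekly pembrolizumab. The confidence interval for the latter, 2.9 to 6.9, includes 3.

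**6. The exponential curve may flatter the plan.** With a 4.1-month median it gives e^(−ln 2 × 6/4.1) = 36% progression-free at 6 months, against 46.4% in Section 2.5. Two illustrations with no loss, HR 0.6435 and assumed uniform accrual over 12 to 24 months:
- 20% of patients with no apparent disease and an assumed 24-month median: 87 to 89 events at 18 months after the last patient.
- A Weibull curve through the two pembrolizumab points (50% at 4.1 months, 46.4% at 6), which leaves 33% of controls event-free at 24 months: about 61 to 63 events at 24 months after the last patient. This is a crude and extreme fit.

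**7. Power by events observed.** Power at d events = Φ(((1 − HR)/(1 + HR))√d − 1.2816). At 96 events: Φ(0.2169 × 9.798 − 1.2816) = 80.1% and Φ(0.1838 × 9.798 − 1.2816) = 69.8%.

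| Events | HR 0.6435 | HR 0.6895 |
|---|---|---|
| 96 | 80.1% | 69.8% |
| 90 | 78.1% | 67.8% |
| 85 | 76.4% | 66.0% |
| 80 | 74.5% | 64.1% |
| 70 | 70.3% | 60.1% |
| 60 | 65.5% | 55.6% |

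**The case against.** Two stronger readings are tempting, and the documents support neither. A reader might infer that 96 is miscalculated; step 1 shows that it is not. A reader might also infer that 96 events cannot be reached; step 3 shows that they can on the plan's own assumptions, and at an assumed 5% yearly loss with a 3-month median the chance is still 92%. The failure risk rests on assumed loss or slower progression. The tables in steps 4 and 5 are ranges, not forecasts.

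Other objections have some force:
- *Leaving treatment is not leaving observation.* Section 4.5 treats the Section 4.4 criteria as removal from study therapy, and Section 8 keeps imaging going until progression. That is right. Only full withdrawal or loss removes an event.
- *Patients with no apparent disease are slow, not event-free.* Also right. They delay the 96th event and lengthen the time over which loss can act.
- *The word evaluable in Section 12.1 may mean that enrolment continues until 100 patients qualify.* It might. But no replacement rule is given, the term is not defined for PFS, and the synopsis and the full analysis set both point to 100 randomised.
- *The sentence sits under Sample Size and may only state the power basis.* Then the document contains no cut-off for the primary analysis, and the same fix applies.
- *A separate SAP may hold a rule.* Possible. The protocol defers only imputation rules to it. If it does hold a cut-off, Section 12.1 should point to it.

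**Conclusion.** The concern holds as a gap in the analysis trigger. Section 12.1 tolerates at most four of 100 patients without an observed event and says nothing about what happens if there are more. That the rule is missing can be read directly from the text. How likely it is to matter cannot: the chance of missing 96 runs from 5% to 98% as the assumed chance of never having an observed event goes from 2% to 10%, with patients independent.

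Section 2.5 gives some reason not to count on a 96% event fraction. It reports a 34% pembrolizumab response rate with 81% of responses maintained after a median 18 months, or 0.34 × 0.81 = 27.5% of patients. That is another population and not a PFS estimate, so it shows direction only.

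The main harm is an analysis date chosen without a rule in an open-label trial. The cost in power depends on the shortfall: about 2 points at 90 events, but about 14 to 15 points at 60. The documents do not settle where in that range the trial would fall. This should be fixed; it does not invalidate the design.

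**What to change.** Replace the sentence on 96 events in Section 12.1 with: *The primary PFS analysis is done at 96 events or at a fixed follow-up after the last patient is randomised, whichever is first.* The sponsor should set the length before any comparison by arm, from its own accrual, loss and disease-status-mix assumptions, and state those assumptions. Add the power table from step 7, down to 60 events. Reconcile the evaluable wording in Section 12.1 with the randomised wording in the synopsis, giving either a replacement rule or a single description.

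The cost is protocol and SAP wording, with no extra patients. The downside is that the stated power becomes conditional on the events observed and may be lower than 80% and 70%, and events after the cut-off do not enter the primary analysis.

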## ***12.2 Blinding and Randomization***

This is an open-label, randomized study. Patients will be randomized to receive immune checkpoint therapy plus dorgenmeltucel-L or immune checkpoint therapy alone in a 1:1 ratio. Patients enrolled in this and later protocol amendments will be stratified by treatment choice and disease status and categorized as follows:

- 1) Patients with unresectable advanced disease
- 2) Patients with resectable advanced disease who receive the immunotherapy in advance of resection
- 3) Patients with resected isolated advanced disease who are treated in a no apparent disease (NAD) state

With sufficient sample size enrolled per disease status category, the randomization process is designed to provide balance between the two treatment arms within each of the disease status categories. The number of patients in each stratum will not be restricted.

Patients enrolled in Protocol Version 1 were not stratified; however the disease status criteria of these patients will be collected to properly account for the randomization strata in the statistical analysis. Further details regarding the randomization procedure are available in the Randomization Plan.

## ***12.3 Statistical Methodology***

Tabulations will be produced for appropriate demographic, baseline, efficacy, and safety parameters. For categorical variables, summary tabulations of the numbers and percentages of patients within each category (with a category for missing data) of the parameter will be presented. Percentages will be based on non-missing data. For continuous variables, the number of subjects, mean, median, standard deviation (StdDev), minimum, and maximum values will be presented. Time-to-event data will be summarized using 25th, 50th (median), and 75th percentiles with associated 2-sided 80% confidence intervals, as well as percentage of censored observations. Quartiles and confidence intervals will be estimated using product-limit (Kaplan-Meier) methodology.

### **Populations to be Analyzed**

The primary population for efficacy will be the full analysis set (FAS), defined as all randomized subjects. In the FAS patients will be analyzed in the treatment group to which they were assigned.

The primary population for safety analyses will be the safety analysis set, defined as all randomized subjects who receive at least one administration of study treatment (dorgenmeltucel-L or immune checkpoint therapy).

### **Demographic and Baseline Characteristics**

Demographic and baseline disease characteristic data summarization will be performed in order to descriptively assess the comparability of dose groups. Data to be tabulated will include sex, age, and race, as well as disease-specific information.

### **Efficacy Analyses**

The primary efficacy endpoint is PFS, where disease progression is defined according to RECIST v1.1. Progression free survival will be summarized using the Kaplan-Meier method of estimation, including the 25th, 50th, and 75th percentiles of time to progression with 95% confidence intervals. Kaplan-Meier plots will be produced by disease status strata to examine the difference in response rates between treatment groups. A stratified log rank test will be applied to test for treatment effect on PFS.

Overall response rate is defined as subjects with a best overall response of at least stable disease. Subjects' best overall response, as determined by the investigator from RECIST, will be summarized by presenting the numbers and percentages of subjects in each response category. The overall response rate will be summarized similarly. Ninety-five percent confidence intervals (CIs) will be constructed for the overall response rate.

The duration of overall response is measured from the time measurement criteria are met for CR or PR (whichever is first recorded) according to RECIST v1.1 until the first date that recurrent or progressive disease is objectively documented (taking as reference for progressive disease the smallest measurements recorded since the treatment started). Duration of overall response will be analyzed in a similar manner to PFS.

Duration of stable disease is measured from the start of the treatment until the criteria for progression are met according to RECIST v1.1, taking as reference the smallest measurements recorded since the treatment started, including the baseline measurements. Duration of stable disease will be analyzed in a similar manner to PFS.

Overall survival is defined as the time to death or last contact and will be summarized in a similar manner to PFS.

As additional secondary endpoints, analysis of PFS, overall response rate, duration of overall response, and duration of stable disease will be repeated using the irRC criteria to identify disease response.

Longitudinal immunological measurements will be analyzed using linear mixed model regression analysis to examine the changes in immunological measurements over time as well as to understand differences between treatment groups in immunological responses over time. An interaction term between disease status category and treatment group will be tested to determine if there is a differential association between strata.

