### 3.2 *Eligibility and On-Study Tests*

Baseline and on-study tests will include (see Section 8.0 Study Calendar):

- Baseline history and complete physical examination
- Serum chemistries including electrolytes, BUN, creatinine, calcium, glucose and albumin; liver function tests including total bilirubin, ALT (SGPT) AST (SGOT), LDH, and alkaline phosphatase; quantitative immunoglobulins (IgG, IgM, and IgE); CBC with platelets and differential.

- Thyroid stimulating hormone (TSH) and free T4.
- Pregnancy testing with serum  $\beta$ -HCG in women of child-bearing potential
- Blood (approximately 16 mL) for measurement of anti-*agal* and anti-tumor antibodies to be drawn on Day 1 before treatment administration and as outlined in Section 8.
- For patients receiving the dorgenmeltucel-L immunotherapy, whole blood (approximately 10 mL) for replication competent retrovirus (RCR) testing on Day 1 prior to the first immunization and will be sent to NewLink Genetics.
- Contrast enhanced CT-scan of the chest and abdomen *or* whole body PET/CT fusion scan. CT-scan or MRI scan of the brain if known or suspected brain metastases. If indicated, CT scan of the neck, *or* ultrasound, PET-scan and/or radionuclide bone scan may also be obtained. PET scans and radionuclide bone scans may not be used for determination of response.
- Measurable disease or solid lesions, liver masses, lymph nodes and skin nodules will be measured and recorded pre-therapy using RECIST/irRC criteria.
- Whole blood (approximately 100 mL) in purple top tubes for PBLs for intracellular cytokines and ELISPOT to be drawn on Day 1 before treatment administration and as outlined in Section 8. These samples will be sent to NewLink Genetics for testing.

Baseline evaluations are to be conducted within 30 days prior to start of protocol therapy unless otherwise specified. In the event that the patient's condition has significantly deteriorated (e.g., significant increase in symptoms or worsening of ECOG PS), laboratory evaluations should be repeated within 5 days prior to initiation of therapy.

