**M Classifications:**

M classification	Site	Serum LDH
M0	No detectable evidence of distant metastases	
M1a	Distant skin, subcutaneous, or nodal mets	Normal
M1b	Lung metastases	Normal
M1c	All other visceral metastases Any distant metastasis	Normal Elevated

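### The primary PFS test leaves out baseline LDH, which is already planned for all patients; adding it as a fixed covariate would gain roughly 1 to 6 points of power if LDH is as prognostic as assumed here

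*Combined protocol and SAP*

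**What the plan says.** **Primary test.** Under Efficacy Analyses in Section 12.3: "A stratified log rank test will be applied to test for treatment effect on PFS". The sentence does not name its strata. Section 12.3 describes no Cox model or covariate-adjusted PFS analysis.

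**Randomisation factors.** Section 12.2 says that patients "will be stratified by treatment choice and disease status and categorized as follows", followed by three disease-status groups. Treatment choice means ipilimumab, nivolumab or pembrolizumab. Protocol Version 1 patients were not stratified, but "the disease status criteria of these patients will be collected to properly account for the randomization strata in the statistical analysis". LDH and M category are not factors.

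**Baseline data.** "Demographic and baseline disease characteristic data summarization will be performed in order to descriptively assess the comparability of dose groups". This is description only.

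**LDH.** Section 3.2 lists among the baseline and on-study tests "liver function tests including total bilirubin, ALT (SGPT) AST (SGOT), LDH, and alkaline phosphatase". LDH is marked pre-study in all five study calendars in the supplied text (Arms 1A, 2A, 2B, 1C and 2C). No Arm 1B calendar appears there, so for that arm the point rests on Section 3.2. In Appendix A the M1c row has two entries, "All other visceral metastases Any distant metastasis", the first paired with normal LDH and the second with elevated LDH.

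**Design.** Section 12.1: 100 patients, 1:1, 96 PFS events, a "two-sided type I error rate of 0.20", and a sample size that "will provide 70% power to detect a hazard ratio of 0.6895" and 80% power at 0.6435.

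**The concern.** The population mixes unresectable, resectable and resected Stage IV disease under three checkpoint inhibitors, and 96 of 100 patients must have an event. When nearly everyone has an event, omitting a prognostic factor pulls the estimated hazard ratio towards 1 and lowers power. The protocol's own staging table treats LDH as bearing on disease severity, and the value is already collected, so using it needs no new data.

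With 50 patients per arm, the arms can also differ noticeably in LDH by chance, and the planned analysis has nothing that corrects for this. Because the study is open-label, an adjustment chosen after such an imbalance had been seen would carry little weight.

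**Working it through.** **1. The plan's own figures.** Two-sided 0.20 gives z = 1.2816; there are 96 events and 1:1 allocation.

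- Schoenfeld: power = Φ(√96/2 × |ln HR| − 1.2816). HR 0.6895: Φ(4.899 × 0.3718 − 1.2816) = 70.5%. HR 0.6435: Φ(4.899 × 0.4408 − 1.2816) = 81.0%.
- Freedman: power = Φ(√96 × (1 − HR)/(1 + HR) − 1.2816). HR 0.6895: 69.8%. HR 0.6435: 80.1%.

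The stated 70% and 80% reproduce. Neither formula allows for differences in prognosis between patients.

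**2. Inputs for the LDH check.** From Section 12.1: N = 100, 96 events, treatment HR 0.6435, control median 3 months. From Section 2.5: 6-month PFS of 46.4% (pembrolizumab every 3 weeks) and 26.5% (ipilimumab), which under exponential PFS give a class hazard ratio of ln 0.464 / ln 0.265 = 0.58. The medians in the same section give 2.8/4.1 = 0.68. The following are assumptions, not in the documents: 60% on PD-1 agents; disease-status mix 70/10/20% with hazard ratios 1/0.8/0.4; 35% with elevated LDH; LDH hazard ratio from 1.0 to 2.5.

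**3. Power with and without LDH.** Both tests are Cox models stratified by disease status with checkpoint class as a covariate. There were 4,000 simulated trials per row, so each power has a standard error of about √(0.75 × 0.25/4,000) = 0.7 points.

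| LDH hazard ratio | Without LDH | With LDH | Gain (points) |
|---|---|---|---|
| 1.0 | 79.5% | 79.4% | −0.1 |
| 1.5 | 77.7% | 79.2% | +1.5 |
| 2.0 | 75.4% | 79.1% | +3.7 |
| 2.5 | 72.2% | 78.3% | +6.1 |

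Two-sided type I error with adjustment was 0.206 at LDH HR 2.0. Without LDH the mean estimated treatment hazard ratio moved to 0.657 (LDH HR 2.0) and 0.669 (2.5). With LDH it stayed at 0.634 to 0.636.

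**4. Against a log-rank stratified by disease status and class.** Log-rank v Cox in the same strata with LDH: 77.6% v 77.3%, 76.2% v 77.5%, 73.6% v 77.0% and 69.8% v 76.3% at LDH HR 1.0, 1.5, 2.0 and 2.5. The gain therefore does not come from adding checkpoint class.

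**5. Sensitivity to the assumptions.** At LDH HR 1.3 the gain is about 0 to 1 point; at 3 it is 6 to 9. If elevated LDH is assumed in 40%, 20% and 5% of unresectable, resectable and resected patients, with both tests stratified by disease status, the gains at LDH HR 1.5, 2.0 and 2.5 are 1.7, 4.6 and 5.8 points for an 80/10/10 disease mix. They fall to 0.9, 2.3 and 4.0 for a 50/20/30 mix.

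**6. Covariate or stratum.** Three agents by three disease states make up to 9 cells. Crossing these with LDH makes up to 18, or 100/18 ≈ 5.6 patients per cell. For the 50/20/30 mix at LDH HR 1.5, the log-rank on the 9 cells has 73.1% power, falling to 70.0% with LDH as a further stratum; a Cox model in the same 9 cells with LDH as a covariate has 74.4%. Across scenarios the extra stratum changes power by about −4 to +4 points.

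**7. Chance imbalance.** With 50 per arm and 35% elevated, the exact binomial probability that the arms differ by at least 10 percentage points is 35%, and by at least 16 points 12%. At LDH HR 2.0 a 16-point difference moves the unadjusted log hazard ratio by about 0.16 × ln 2 = 0.11. That is a factor of about 1.12, or 0.54 standard errors (2/√96 = 0.204).

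**The case against.** A stratified log-rank on the randomisation factors is a standard primary test and matches the sample-size basis, which reproduces. In a 100-patient phase 2b trial at two-sided 0.20, choosing LDH rather than performance status or visceral disease is a judgement, and adjustment makes the hazard ratio conditional. All of this stands, and it limits the point to efficiency and robustness.

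Four stronger readings are tempting, and the documents do not support them.

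- *The log-rank test is invalid.* It is not. Randomisation protects its type I error, and chance imbalance is a matter of precision.
- *The 80% power in Section 12.1 is wrong.* It follows from its stated inputs. How far real power falls below it depends on prognostic effects that the documents do not give.
- *LDH alone defines M1c.* Other visceral metastases are M1c with normal LDH, and a staging table gives no PFS effect size.
- *The benefit equals about 20% more events.* That figure comes from comparing a log-rank stratified by disease status only with a model that adds both checkpoint class and LDH (71.4% v 77.1% at LDH HR 2.0): ((1.2816 + 0.742)/(1.2816 + 0.565))² = 1.20. For LDH alone (73.5% v 77.1%) it is ((1.2816 + 0.742)/(1.2816 + 0.628))² = 1.12.

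A further fair objection is that a model with LDH but without checkpoint choice would drop a randomisation factor. At LDH HR 1.5 such a model had 75.7% power, against 78.3% with class included. The fix must therefore keep both factors.

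**Conclusion.** The point holds as one of efficiency and robustness. The primary PFS test uses no covariate, although LDH is a planned baseline measurement for all patients. If about 35% have elevated LDH and its PFS hazard ratio is 1.5 to 2.5, adjustment gains roughly 1 to 6 points of power at HR 0.6435. A reader should not take that range as a known loss, because prevalence, LDH hazard ratio, disease mix and agent mix are all assumed. What depends little on them is the asymmetry: essentially no power is lost if LDH proves irrelevant, a few points are gained if it matters, and the result is protected against LDH imbalance. Type I error stays near 0.20.

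**What to change.** In Section 12.3, make the primary PFS test a Cox model at two-sided 0.20 that:

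- accounts for both randomisation factors, stratified by disease status with checkpoint inhibitor choice as a covariate or stratum;
- includes baseline LDH (above the upper limit of normal v not) as a fixed covariate, not as an additional stratum;
- states a rule for missing LDH, such as a missing-value indicator. The Missing Data section makes no substitutions in general, and the full analysis set is all randomised patients, so without a rule patients could drop out of the primary test.

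Keep the stratified log-rank as a sensitivity analysis and name its strata. Fix the model in the protocol and SAP now, before any comparative outcome data are reviewed, because the trial is open-label.

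The cost is wording: no new data, visits or patients. The small downside is that the reported hazard ratio is conditional on LDH, which the report should say.
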